9.6.5 Laboratory Test Results

Summary statistics for baseline, minimum on study, maximum on study, EOTP, and change from baseline to EOTP by treatment group will be provided for:

- Hemoglobin
- Platelets
- White blood cell count
- Serum ferritin
- Serum iron
- Transferrin saturation level (TSAT)
- Total iron binding capacity
- Creatinine
- Total bilirubin
- Alanine aminotransferase (ALT), and
- Aspartate aminotransferase (AST).

Summary statistics will not be **generated for** the other hematology or analytes reported by the central laboratory but the data will be captured in the electronic line listings.

In addition, summary statistics for the average of all post-baseline hemoglobin values will be provided by treatment group (summarized both by keeping and **excluding** hemoglobin values that occurred within 28 days **following** a RBC transfusion).

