EpoR	Erythropoietin receptor
ESA	Erythropoiesis stimulating agent
FDA	Food and Drug Administration
FDG-PET	Fluorodeoxyglucose-PET
g/dL	Gram per deciliter
GBG	German Breast Group
GGT	Gamma-glutamyltransferase
GOG	Gynecologic Oncology Group
HIV	Human immunodeficiency virus
HR	Hazard ratio
HSA-free	Human serum albumin-free
ICF	Informed consent form
ICH GCP	International Conference on Harmonisation Tripartite Guideline on Good Clinical Practice
ID	Identification
IEC/IRB	Independent ethics committee/institutional review board
IP	Investigational product
IV	Intravenous
IVR/IWR System	Interactive Voice Response/Interactive Web Response System
PPD	
kg	Kilogram
LDH	Lactate dehydrogenase
LTFU	Long-term follow-up
MCH	Mean corpuscular hemoglobin
MCHC	Mean corpuscular hemoglobin concentration
MCV	Mean corpuscular volume
MDS	Myelodysplastic syndromes
mL	Milliliter
MRI	Magnetic resonance imaging

Abbreviation or Term	Definition/Explanation
NA	Not applicable
NE	Inevaluable
ng	Nanogram
NSCLC	Non-small cell lung cancer
ODAC	Oncologic Drug Advisory Committee
OR	Odds ratio
OS	Overall survival
PD	Progressive disease
PE	Physical examination or pulmonary embolism
PET	Positron emission tomography
PET-CT	Positron emission tomography-computer tomography
PFS	Progression-free survival
pg	Picogram
PICC	Peripherally-inserted central catheter
PIN	Personal identification number
PR	Partial response
Q3M	Once-every-3-months
Q3W	Once-every-3-weeks
Q9W	Once-every-9-weeks
QW	Once-weekly
RBC	Red blood cell
RECIST	Response evaluation criteria in solid tumors
rHuEPO	Recombinant human erythropoietin
SAE	Serious adverse events
SAER	Serious adverse event report
SCLC	Small cell lung cancer
Screening hemoglobin	Local laboratory hemoglobin; sample obtained within 7 days prior to randomization
Screening period	Starts when the subject signs and dates the informed consent form and ends when the subject is randomized or screen failed. Must not exceed 21 days.
SD	Stable disease
SUSAR	Suspected unexpected serious adverse reactions
TIA	Transient ischemic attack
TIBC	Total iron binding capacity
Tsat	Transferrin saturation

Abbreviation or Term	Definition/Explanation
Treatment period	Starts when the subject is randomized and ends at the next Q3W visit after disease progression has been determined (EOTP). Note that EOTP is based on disease progression, not IP dosing.
TVE	Thrombovascular event
μg	microgram
ULN	Upper limit of normal
US	Ultrasound
VTE	Venous thromboembolic event
WBC	White blood cell
Wk	Week

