7.5 Treatment Period (Q3W Visits)

Study visits will occur every 3 weeks \pm 6 days with subcutaneous IP administration Q3W during the treatment period. IP will be discontinued within 3 weeks after the last dose of chemotherapy, or upon the determination of disease progression, whichever occurs first.

For all study visits during the treatment period, study procedures (eg, ECOG, laboratory sample draws) may be performed up to 1 day prior to IP dosing.

The following assessments and procedures will be performed during the treatment period:

- Vital signs and weight
- · The presence of a central or mid-line venous catheter
- ECOG performance status
- Assessment of disease progression
- Assess for signs and symptoms of clinically relevant TVE. If present, perform appropriate laboratory, diagnostic, and medical imaging for suspected TVE
- Imaging studies Q9W (or earlier if clinically indicated) until documented disease progression (see Section 7.1.6)
- Central laboratory tests: clinical chemistries and CBC with differential (including hemoglobin for statistical analyses), Tsat, ferritin, iron, and TIBC. Central laboratory tests will continue until the next Q3W study visit that occurs after the last dose of IP
- Local laboratory hemoglobin for IP dosing determination. Local laboratory hemoglobin testing will continue until the next Q3W study visit that occurs after the last dose of IP
- Access IVR/IWR system for medication assignment or to register a subject's discontinuation from IP (if applicable)
- Subcutaneous Q3W administration of IP
- Subjects who discontinued IP but have not had disease progression will continue Q3W visits and Q9W imaging studies until disease progression has been determined. Subjects who are unable to continue Q3W visits and Q9W imaging studies until disease progression should complete EOTP procedures at no later than their next Q3W visit and will be asked to enter the LTFU period

Concomitant medications, radiotherapy, anti-cancer therapy, anti-cancer surgery, and RBC transfusion information will be collected throughout the treatment period. AEs and SAEs will be collected up to 30 days after the last dose of IP.

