7.6 End of Treatment Period

Subjects will complete the EOTP visit at the next Q3W visit (± 6 days) after disease progression has been determined either by imaging studies or by clinical assessments in the absence of imaging confirmation. Subjects who are unable to continue Q3W visits and Q9W imaging studies until disease progression should complete EOTP procedures

at no later than their next Q3W visit (\pm 6 days). At the time of the EOTP visit, any subject who has experienced a serious and treatment related adverse event during the study, as determined by the investigator, will continue to be followed for that event, until the event is resolved or considered stable; all EOTP visit procedures may still be conducted prior to resolution.

The following EOTP assessments and procedures will be required for all subjects:

- Vital signs and weight
- The presence of a central or mid-line venous catheter
- ECOG performance status
- Assess for signs and symptoms of clinically relevant TVE. If present, perform appropriate laboratory, diagnostic, and medical imaging for suspected TVE
- Adverse events, concomitant medications, radiotherapy, anti-cancer therapy, anticancer surgery, and RBC transfusions
- Central laboratory serum chemistries and CBC with differential (including hemoglobin for statistical analyses) (except if EOTP visit occurs following the Q3W visit after the last dose of IP)
- Local laboratory hemoglobin (except if EOTP visit occurs following the Q3W visit after the last dose of IP)
- Darbepoetin alfa antibody

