15. APPENDICES

	Screening ^a	Screening ^a Treatment Period ⁿ			EOTP Visit	LTFU ^m
Study Week	-3	Day 1 / Wk 1	Q3W (± 6 days) (eg, Wk 4, 7, 10, 13, 16, 19, 22, 25, 28)	Last dose of IP	Next Q3W visit after disease progression	Every 3 months (± 2 weeks)
Informed consent, medical history, and complete physical exam	х					
Vital signs ; other ^b	Х	Х	Х	X X		
ECOG performance status	Х	Х	Х	Х	Х	
Adverse events ^c , concomitant meds and RBC transfusions						
Tumor evaluation and assessment of disease progression					► ►	
Investigational product administration ^d		Х	Х	Х		
Lab testing						
Central lab clinical chemistries ^e	Х	Х	Х	Х	X °	
Central lab CBC ^f	Х	Х	Х	Х	X°	
Local lab hemoglobin ^g	Х	Х	Х	Х	X°	
Central lab serum folate and vitamin B ₁₂	Х					
Central lab iron studies ^h	Х	Х	Х	Х		
Tumor samples ⁱ	Х					
Darbepoetin alfa antibody ^j		Х			Х	
Endogenous erythropoietin level		Х				
Central lab pregnancy test ^k	Х					
Imaging studies						
CT scan, MRI, or PET-CT ¹	Х	Every 9 weeks until disease progression (eg, Wk 10, 19, 28)				
LTFU						
Collect information on survival, ESA usage, anti-cancer therapy, radiotherapy, anti-cancer surgery						х

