- g. The hemoglobin sample to confirm eligibility must be obtained within 7 days prior to randomization. During the treatment period, the hemoglobin sample for dosing decisions / adjustments may be obtained on the day of IP dosing or up to 1 day prior to the day of IP dosing.
- h. Central lab iron studies consist of serum iron, ferritin, TIBC, and Tsat%. Only soluble transferrin receptor will be performed at Day 1. Iron, ferritin, Tsat%, and TIBC will be performed Q3W.
- i. If available, paraffin embedded tumor block or unstained slides from previous biopsy, along with the matching pathology report will be collected during screening
- j. Serum antibody samples must be collected pre-dose.
- k. Central lab pregnancy testing performed for all female subjects of reproductive potential.
- I. Subjects must have had a baseline scan (CT, MRI, or PET-CT) of the chest to assess disease burden before starting on first line chemotherapy for NSCLC and the images must be reviewed by the investigator prior to randomization. Images to assess disease status will be obtained Q9W (or sooner if clinically indicated) from Week 1 until disease progression using the same type of scan as at baseline. Bone scans, MRI, CT, PET, PET/CT, or X-ray will be performed when signs or symptoms suggestive of bone metastasis are present, and positive bone scans or PET scans must be confirmed by another imaging method (ie, X-ray, CT or MRI). Once disease progression has been determined, imaging studies are no longer required.
- m. Subjects will be followed in LTFU for survival until death, or until approximately 2700 deaths have occurred on the study (End of Study).
- n. The treatment period starts when the subject is randomized and ends at the next Q3W visit after disease progression has been determined (EOTP). Note that EOTP is based on disease progression, not IP dosing. All study visits during the treatment period may occur over a 2 consecutive day period. Study procedures (eg, ECOG, laboratory sample draws) may be performed up to 1 day prior to IP dosing.
- o. Central lab clinical chemistries, central lab CBC and local lab hemoglobin tests are not performed if the EOTP visit occurs following the Q3W visit after the last dose of IP.

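### SAP 9.6.5 takes laboratory change from baseline at EOTP, a visit at which the protocol lists no iron studies and waives chemistries and blood counts for many subjects

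*SAP*

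**What the plan says.** SAP 9.6.5, repeated in the Clinical Laboratory row of the safety endpoint table in SAP 9.6, states: "Summary statistics for baseline, minimum on study, maximum on study, EOTP, and change from baseline to EOTP by treatment group will be provided for". The 11 analytes in question are hemoglobin, platelets, white cells, ferritin, iron, TSAT, TIBC, creatinine, total bilirubin, ALT and AST. SAP Appendix A treats EOTP as an actual visit, the next three-weekly visit after progression.

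The protocol's Study Glossary and Appendix A (footnote n) say of that visit: "Note that EOTP is based on disease progression, not IP dosing". Laboratory sampling follows a different clock. Protocol 7.5 says: "Central laboratory tests will continue until the next Q3W study visit that occurs after the last dose of IP". Protocol 7.6 requires chemistries, CBC and local hemoglobin at EOTP, "except if EOTP visit occurs following the Q3W visit after the last dose of IP", and footnote o of Appendix A repeats the waiver: "tests are not performed if the EOTP visit occurs following the Q3W visit after the last dose of IP".

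Iron studies are missing from the EOTP list in protocol 7.6. In Appendix A the row "Central lab iron studies" is marked up to the last dose of IP and has no mark under EOTP. Footnote h says only: "Iron, ferritin, Tsat%, and TIBC will be performed Q3W".

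**The concern.** The analysis asks for a value at a visit timed by progression, while the samples stop at a visit timed by the last IP dose. Under protocol 3.1, IP ends within three weeks of the last chemotherapy dose even if the disease has not progressed. A subject who finishes chemotherapy and progresses several visits later therefore reaches EOTP with no scheduled laboratory draw.

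The SAP has no rule for this. Its last-available-value rule (SAP 8.3.4) covers only hemoglobin change to the end of the efficacy treatment period (EOETP). The hemoglobin change definition in SAP Section 5 adds weeks 13 and 16 because EOETP varies by subject. The other ten analytes get neither provision.

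At stake is the reading of a long-term safety trial's laboratory tables. A change column invites comparison between arms, but its contributors are chosen by what happens after randomization, and the SAP does not require the number contributing to be shown.

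**Working it through.** The plan gives no figure on this point to reproduce. The check sets the sampling schedule against the analysis time point, then gauges how wide the gap could be.

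**Step 1: iron, ferritin, TSAT, TIBC.** The protocol 7.6 list, the Appendix A row and footnote o all leave these out at EOTP. Protocol 7.5 groups them with the central tests that run to the first three-weekly visit after the last IP dose. If that visit is also EOTP, 7.5 could be read as giving a draw. No other route to an EOTP value exists.

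**Step 2: the other seven analytes.** A draw is scheduled only if EOTP is no later than the first three-weekly visit after the last IP dose. Three cases follow:

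- Progression is determined between visits while on IP: the next visit is both EOTP and the first visit after the last dose, so there is a draw.
- Progression is determined at a three-weekly visit before dosing: that visit is already the first after the last dose and EOTP is the one after it, so the draw is waived. Appendix A's example imaging weeks (10, 19, 28) coincide with its example visit weeks, so this can happen to subjects who progress while on IP.
- Chemotherapy ends and progression comes more than one visit after the last IP dose: the draw is waived.

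**Step 3: which analytes have another change summary.** Hemoglobin also has change to EOETP, week 13 and week 16 (SAP Section 5 and the efficacy endpoint table). The other 11 − 1 = 10 have change to EOTP only.

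**Step 4: scale.** The documents give neither an expected PFS nor a duration of IP. Protocol 4.1.1 gives only an expected minimum of two further cycles (six weeks). As assumptions, take IP for 6 to 36 weeks and exponential PFS with median 3 to 8 months. The share alive and progression-free when IP ends is 0.5^(t/m), with t = weeks ÷ 4.348 (365.25/12/7 weeks per month).

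- Lowest: t = 36/4.348 = 8.28 months, m = 3, giving 0.5^2.76 = 0.148, about 15%.
- Highest: t = 6/4.348 = 1.38 months, m = 8, giving 0.5^0.1725 = 0.887, about 89%.

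| IP duration | Median 3 mo | 4.5 mo | 6 mo | 8 mo |
|---|---|---|---|---|
| 6 weeks | 73% | 81% | 85% | 89% |
| 12 weeks | 53% | 65% | 73% | 79% |
| 18 weeks | 38% | 53% | 62% | 70% |
| 24 weeks | 28% | 43% | 53% | 62% |
| 36 weeks | 15% | 28% | 38% | 49% |

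These shares only approximate the proportion without an EOTP draw. Subjects who die before an EOTP visit, and those in the second case of Step 2, add to it. Subjects who progress within one visit of the last IP dose, or who stop attending soon after it, reduce it.

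**The case against.** **Scope.** A reader might infer that the whole safety-laboratory comparison is empty or confined to early progressors. It is not. Minimum and maximum on study are planned for all 11 analytes and need no EOTP sample. Hemoglobin also has an average post-baseline value, the change summaries in Step 3, and the threshold and rate-of-rise summaries. Contributors are not only early progressors either: protocol 6.2.2 allows IP during myelosuppressive maintenance, so a late progressor can have an EOTP draw, and protocol 7.6 has subjects who cannot continue visits complete EOTP without progression. All of this stands.

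**Iron.** Protocol 7.5 can be read as yielding an iron value at some EOTP visits, so a flat zero is too strong. The extracted Appendix A table is also damaged, and its columns alone are weak evidence. But the EOTP list and footnote o, both plain text, omit iron studies as well.

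**Typical subjects.** The inference that most subjects lack an EOTP draw is plausible for many inputs, but the documents do not establish it.

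**Bias between arms.** Hemoglobin-driven dosing rules could shift the last IP dose differently by arm. However, temporary withholding need not make a dose the last one, and non-responders switched to placebo are still receiving IP. Only discontinuation after three dose reductions clearly moves the last dose, and its frequency is not given. A difference between arms is possible but not shown.

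**Consequence.** The tables are descriptive, lie outside the testing hierarchy, and use the safety set by actual treatment. That limits the harm but does not supply the missing end value.

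**Conclusion.** The mismatch is real and follows from the text without assumptions. As written, the EOTP and change-to-EOTP columns would hold few or no values for the four iron analytes. For the other seven they would hold values only from subjects whose EOTP fell no later than the first three-weekly visit after the last IP dose. That selection happens after randomization and depends on when progression, or withdrawal from visits, falls relative to the last dose.

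The size of the selected group is open. The 15% to 89% range rests wholly on assumed IP durations and PFS medians and shows only that the gap could be modest or large. OS, PFS and the transfusion endpoint are unaffected. The SAP should be changed here because the plan names a value that is often not collected while a suitable one already is.

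**What to change.** In SAP 9.6.5 and the Clinical Laboratory row of the safety endpoint table, replace EOTP for laboratory analytes by the last post-baseline central-laboratory value up to and including the first three-weekly visit after the last IP dose. Keep minimum and maximum on study. Report the number of subjects contributing per analyte and arm.

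EOETP with a stated last-available rule, or fixed weeks such as 13 and 16, would also repair the column. The proposed value is preferred because it matches the point at which protocol 7.5 ends central testing.

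The cost is SAP wording and one changed visit derivation, with no new samples. There are two drawbacks. The laboratory time point would differ from the EOTP convention kept for vital signs, weight and ECOG. It would also still vary between subjects, so the table should be labelled as an end-of-IP summary.

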9.6.6 Vital Signs

Summary statistics for baseline, minimum on study, maximum on study, EOTP, and change from baseline to EOTP by treatment group will be limited to:

- Systolic blood pressure,
- Diastolic blood pressure, and;
- Pulse

No other vital signs data will be summarized but the data will be captured in the electronic line listings.

Eastern Cooperative Oncology Group (ECOG) performance status scores will be summarized for each treatment group at baseline, EOTP and change from baseline to EOTP.

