10. STATISTICAL CONSIDERATIONS

10.1 Study Design

This is a double-blind, randomized, placebo-controlled, phase 3 non-inferiority study in CIA subjects receiving multi-cycle chemotherapy for the treatment of stage IV NSCLC cancer. Randomization will occur in a 2 to 1 ratio (darbepoetin alfa to placebo) and will be stratified by geographic region, histology (squamous versus other), and screening hemoglobin (< 10.0 g/dL versus \ge 10.0 g/dL). Subjects will receive IP Q3W during the treatment period. IP will be discontinued within 3 weeks after the last dose of chemotherapy, or upon the determination of disease progression, whichever occurs first. Study visits Q3W and imaging studies Q9W will occur during the treatment period until disease progression. The EOTP visit will occur at the next Q3W visit after disease progression has been determined. Subjects will then enter long-term follow-up and will be followed for survival until death, or until approximately 2700 deaths have occurred.

The primary objective of the study is to demonstrate that subjects treated with darbepoetin alfa to a hemoglobin ceiling of 12 g/dL is non-inferior to subjects on placebo with respect to survival. Key secondary objectives include demonstrating that subjects treated with darbepoetin alfa to a hemoglobin ceiling of 12 g/dL is non-inferior to subjects on placebo with respect to PFS and demonstrating that darbepoetin alfa is superior to placebo with respect to transfusions.

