Cerebrovascular disorders	Central nervous system vascular	Narrow
	disorders SMQ	
Hypertension	Hypertension SMQ	Narrow
Cardiac failure	Cardiac failure SMQ	Narrow
Thromboembolic events, venous	Embolic and thrombotic events,	Narrow
	venous	
Convulsions	Convulsions SMQ	Narrow & Broad
Severe cutaneous reactions	Severe cutaneous reactions SMQ	Narrow & Broad
Hypersensitivity	Hypersensitivity SMQ	Narrow & Broad
PRCA	Antibody-mediated Pure Red Cell Aplasia AMQ	

Events of Interest (EOI): EOIs for Aranesp are as follows:

Hemoglobin Threshold

A hemoglobin that increases to >12 g/dL at any time during the treatment period is considered to have exceeded the threshold. This increase will be summarized both by including and excluding hemoglobin values that occurred in the 28-day period following an RBC transfusion.

Medications of Interest (MOI): MOIs for Aranesp Oncology are as follows based on values as of **Q2 2017** or later:

Antihypertensives
Antimicrobials
Antithrombotic agents
Colony stimulating factors
Epoetins
Histone deacylating inhibitors
Hypomethylating agents
Iron
Iron chelating agents
Lenalidomide
Methotrexates
Platelets
Platelets Thalidomide

Non-response (to investigational product)

A non-responder is a subject who, after study day 35, received two transfusions that are \geq 21 days apart and \leq 42 days apart.

Objective tumor response rate (ORR)

The incidence of a complete or partial response at any time during the study. Response will be determined by the investigator's assessment of the scans using the version of RECIST specified in the protocol at the time of subject enrollment.

Overall survival (OS)

Time from randomization to date of death. Subjects will be censored on the date of last contact (ie, the date the subject was last known to be alive) if they are not known to be dead.

Progression-free survival (PFS)

Time from randomization to date of radiographic disease progression or death from any cause, whichever event occurs first. Subjects without either event will be censored on the date of their last disease assessment. Disease progression will be based on the investigator's assessment of scans using the version of RECIST specified in the protocol at the time of subject enrollment.

Rate of rise in hemoglobin >1.5 g/dL in 21 days

The occurrence of a hemoglobin that increases by >1.5 g/dL in any 21-day period in the treatment

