Clinical Laboratory	Summary statistics for baseline, minimum on study, maximum on study, EOTP, and change from baseline to EOTP by treatment group will be provided for: Hemoglobin Platelets White blood cell count Serum ferritin Serum iron Transferrin saturation level (TSAT) Total iron binding capacity Creatinine Total bilirubin Alanine aminotransferase (ALT), and Aspartate aminotransferase (AST) 	N/A Note: data for all other analytes will be provided in an electronic format
Summary of Hemoglobin	Summarize the number and percent of subjects who had hemoglobin > 12.0	

Threshold – Primary Analysis Set	g/dL at any time in the treatment period (both adjusting and not adjusting for RBC transfusions) by treatment group Dataset: Safety Analysis Set	
Summary of Rapid Rate of Rise in Hemoglobin – Primary Analysis Set	Summarize the number and percent of subjects who had a rapid rate of rise in hemoglobin (> 1.5 g/dL in 21 days) at any time in the treatment period (both adjusting and not adjusting for RBC transfusions) by treatment group Dataset: Safety Analysis Set	
Summary of Non-response to Investigational Product – Primary Analysis Set	Summarize the number and percent of subjects who were non-responders by treatment group Dataset: Safety Analysis Set	
Antibody Result	s, Vital Signs, ECOG	
Summary of Antibody Results –	Summarize antibody results for darbepoetin alfa by treatment group Dataset: Safety Analysis Set	 Summarize antibody results for erythropoetin by treatment group Dataset: Safety Analysis Set
Summary of Vital Signs	Summarize weight, systolic blood pressure, diastolic blood pressure, pulse by treatment group Dataset: Safety Analysis Set	
Summary of ECOG Performance Status	Summarize ECOG by treatment group Dataset: Safety Analysis Set	

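### The only planned blood pressure change score is baseline to EOTP, a visit set by progression after IP has stopped; add on-treatment changes from data already collected

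*SAP*

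**What the plan says.** SAP 9.6.6 covers systolic pressure, diastolic pressure and pulse: "Summary statistics for baseline, minimum on study, maximum on study, EOTP, and change from baseline to EOTP by treatment group will be limited to" these three. Other vital signs data go only to electronic listings. The vital-signs row of the safety endpoint table in SAP 9.6 names no time point: "Summarize weight, systolic blood pressure, diastolic blood pressure, pulse by treatment group".

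Protocol 10.1 fixes the timing of EOTP: "The EOTP visit will occur at the next Q3W visit after disease progression has been determined". Protocol Appendix A, footnote n, is explicit: "Note that EOTP is based on disease progression, not IP dosing". On dosing, Protocol 10.1 says "IP will be discontinued within 3 weeks after the last dose of chemotherapy, or upon the determination of disease progression, whichever occurs first". After that, Protocol 7.5 keeps the visits going: "Subjects who discontinued IP but have not had disease progression will continue Q3W visits and Q9W imaging studies until disease progression has been determined". The list of treatment-period procedures in the same section includes "Vital signs and weight", so blood pressure is recorded at the Q3W dosing visits and also at the visits after IP has ended.

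Hypertension is a listed event of interest in SAP section 5 ("Hypertension SMQ", narrow scope), and antihypertensives are a medication of interest in SAP Appendix B.

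**The concern.** A change score for a safety variable is most useful when it is taken while the subject is exposed. Here the one change score is tied to a visit that the protocol separates from dosing. If darbepoetin alfa raises blood pressure during treatment and the rise recedes after the last dose, the EOTP contrast will show less of it than was present on treatment. A small difference at EOTP could then be read as reassurance about blood pressure on treatment, which that contrast does not measure.

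Only the interpretation of one descriptive safety table is at stake. OS, PFS and the transfusion endpoint are unaffected.

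**Working it through.** The plan states no blood pressure effect, standard deviation or expected gap, so there is no figure to reproduce. The check is of timing.

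**1. Order of events.** Let L be the day of the last IP dose, P the day progression is determined and E the EOTP visit. Under Protocol 10.1, IP has ended by P at the latest and E is the next Q3W visit after P. The gap is E − L = (P − L) + (E − P).

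- E − P is at most one visit interval, nominally 21 days, with a ± 6 day window.
- P − L is short for subjects treated up to progression. For subjects who complete chemotherapy first, the plan sets no upper limit.

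**2. Day counts on the nominal schedule** (doses on days 1, 22, 43, 64 and so on, SAP Appendix A). These illustrate the rule and say nothing about how often each path occurs.

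- Dose on day 43, progression found between visits: EOTP on day 64, and 64 − 43 = 21 days.
- Last dose on day 43, progression found at the week 10 scan visit (day 64) and no IP given: EOTP on day 85, and 85 − 43 = 42 days.
- IP ended with chemotherapy and no progression: each further Q9W scan interval without progression adds 9 × 7 = 63 days.

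**3. What counts as on treatment.** Protocol section 7 has visit assessments done before IP is given, so an ordinary on-treatment reading is itself taken about 21 days after the previous dose. An EOTP reading in the first case has the same lag. The problem therefore lies with subjects whose gap is longer than one dosing interval.

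**4. Direction and size.** If an on-drug rise persists after IP, the EOTP change is not attenuated. If it fades, the change is attenuated. The amount depends on the distribution of E − L, the on-drug effect and how quickly it fades. The documents give none of these, so no number follows.

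**5. How the SAP handles hemoglobin.** SAP section 5 takes the change in hemoglobin to EOETP, which is tied to the last dose of IP or chemotherapy. Because EOETP varies between subjects, it also reports the change at weeks 13 and 16. The protocol also foresees a late EOTP: section 7.6 and Appendix A, footnote o, omit central chemistry, CBC and local hemoglobin when EOTP comes after the first Q3W visit following the last dose. Blood pressure has neither a dose-tied endpoint nor fixed visits.

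**6. Effect of the non-responder switch on an on-IP window.** Protocol 6.1.2 moves darbepoetin non-responders to placebo, which also counts as IP. The rule needs two transfusions after study day 35 that are at least 21 days apart, so the earliest possible day is 36 + 21 = 57. The week 7 window in SAP Appendix A closes on day 49. Weeks 4 and 7 therefore precede any switch; later columns may include switched subjects.

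**The case against.** The strongest reply is that the sentence in SAP 9.6.6 also plans the maximum on study by treatment group. Because vital signs are taken at every Q3W visit, that maximum includes the on-drug readings. Hypertension events are tabulated in a window tied to dosing (day 1 to 30 days after the last IP dose, SAP section 5), and antihypertensive use is summarized by arm. A null change at EOTP would not be read alone. Some subjects also have a short gap: those who progress on drug, those who stay on IP through myelosuppressive maintenance, and those who cannot continue visits and complete EOTP no later than the next Q3W visit.

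All of this stands, and it limits the point to the change score. A reader might infer that the whole plan measures blood pressure off drug; the planned maximum and the event tables contradict that. A reader might also want to put a figure on the dilution, or argue that the maximum is biased because it rises with the number of visits. The documents supply no inputs for the first. For the second, the comparison is between randomized arms, so a visit-count effect largely cancels if time to progression is similar, and nothing in the documents shows an imbalance. Nor do the documents quantify any blood pressure effect of darbepoetin alfa.

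The reply does not remove the gap in the plan. The maximum is an absolute level, not a change, and it is not restricted to visits on IP. The event tables count reported events, not a shift in measured pressure.

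A note in SAP Appendix A says that study drug administration should last until progression. Read alone, it would keep EOTP near the last dose for everyone. It differs from SAP 3.1 and Protocol 10.1, and the passages should be reconciled. The reasoning here follows the rule that 3.1 and 10.1 share.

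**Conclusion.** The point holds in a limited form. The only planned blood pressure change score is taken after IP has stopped, at a visit set by progression, with no upper limit on the interval since the last dose. It would understate a rise that fades off drug. That direction rests on one assumption, that the effect recedes after dosing ends. The size cannot be derived from the documents and none is claimed. On-treatment signals are still partly captured elsewhere. This is a minor improvement to a descriptive table and has no bearing on the primary or secondary conclusions.

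**What to change.** In SAP 9.6.6 and the vital-signs row of the safety endpoint table:

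- Add change from baseline in systolic and diastolic pressure at weeks 4, 7, 10, 13 and 16 among subjects still receiving IP.
- Add change from baseline at the last visit within 21 (+6) days of the last IP dose.
- Report the maximum restricted to visits up to that date.
- Keep EOTP as a secondary column.
- Footnote that darbepoetin non-responders switched to placebo count as on IP, and that the week 4 and 7 columns precede any such switch.

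A tabulation of the percentage above 160/100 mmHg is optional. That level is an eligibility criterion in Protocol 4.2.1 and would serve here only as a descriptive cut.

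The change needs SAP wording and a re-windowed table. It needs no new data, no new visits and no change in patient management. The downside is a longer table, with fewer subjects at later weeks.
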